11. OVERVIEW OF ASSESSMENTS

The assessments supporting the objectives for the study are in Table 7:

Table 7: Table of Assessments

Primary Objectives	Assessments
PK parameters	OCA and its conjugates glyco-OCA and tauro-OCA, and metabolite OCA glucuronide
Safety and tolerability	SAEs and TEAEs, physical exam, ECG, vital signs, clinical laboratory assessments, discontinuations, pruritus, and fatigue
Secondary Objectives	Assessments
Changes in risk scores	Changes in MELD and in CP Scores and components of the CP score and MELD score
Changes in liver biochemistry and hepatobiliary damage	Total and direct bilirubin, ALP, ALT, AST, GGT, INR, creatinine, albumin, platelets
PD parameters	FGF-19, C4, and plasma bile acids
Additional Objectives	Assessments
Noninvasive measurements of liver fibrosis, liver stiffness and cirrhosis	TE/ELF (HA, P3NP, and TIMP-1)
PK/PD relationship	PK parameters compared to PD parameters and safety and tolerability assessments (above)
Patient-reported outcomes	Pruritus VAS, PBC-40, EQ-5D-5L, CLDQ
Clinical events	Death (all-cause and liver-related), liver transplant, MELD score ≥ 15 (for patients with MELD ≤ 12 at baseline), hospitalization for new onset or recurrence of: variceal bleed, hepatic encephalopathy, spontaneous bacterial peritonitis, uncontrolled ascites, and HCC.

ALP = alkaline phosphatase; ALT = alanine aminotransferase; AST = aspartate aminotransferase;
C4 = 7 α -hydroxy-4-cholesten-3-one; CLDQ = Chronic Liver Disease Questionnaire; CP = Child-Pugh; ECG =
electrocardiogram; ELF = enhanced liver fibrosis;
FGF-19 = fibroblast growth factor-19; GGT = gamma-glutamyl transferase; HA = hyaluronic acid;
INR = international normalized ratio; MELD = Model End Stage Liver Disease; OCA = obeticholic acid; P3NP =
procollagen 3 N-terminal peptide; PBC = Primary Biliary Cholangitis;
PD = pharmacodynamic; PK = pharmacokinetic; SAE = serious adverse event; TE = Transient Elastography;
TEAE = treatment emergent adverse events; TIMP-1 = tissue inhibitor of metalloproteinase 1; VAS = visual
analog scale

12. CLINICAL PHARMACOKINETIC ASSESSMENTS

Pharmacokinetic analyses will be based on the PK population ([Section 15.1](#)). Patients in the PK Population with at least one PD assessment after dosing will be included in the combined PK/PD analyses.

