6.3. Additional Objectives

- To evaluate the effect of OCA treatment compared to placebo on:
 - Noninvasive markers of liver fibrosis (Enhanced Liver Fibrosis [ELF]TM score)
 - Noninvasive measurement of liver stiffness (transient elastography [TE])
- To assess the PK/Pharmacodynamic (PD) relationship of OCA with:
 - PK parameters compared to PD parameters and safety and tolerability assessments
- To assess patient reported outcomes (Pruritus Visual Analogue Scale [VAS], PBC-40, EQ 5D-5L, Chronic Liver Disease Questionnaire [CLDQ])

- To assess clinical events consistent with end-stage liver disease
 - Death (all cause)
 - Liver transplant
 - MELD score ≥ 15 (for patients with MELD ≤ 12 at baseline)
 - Hospitalization (as defined by a stay of 24 hours or greater) for new onset or recurrence of: variceal bleed, hepatic encephalopathy (as defined by a West Haven score of ≥ 2), spontaneous bacterial peritonitis
 - Uncontrolled ascites (diuretic resistant ascites requiring therapeutic paracentesis at a frequency of at least twice in a month)
 - Hepatocellular carcinoma (HCC)

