7.3. Planned Dosing Regimen

All patients will initiate investigational product once weekly with OCA 5 mg or matching placebo (Table 2). Titration may be considered as early as the Week 12 Visit. Following visit procedures at Week 12, if the investigational product is tolerated and laboratory assessments do not indicate a safety concern, the patient may up-titrate to OCA 5 mg twice weekly and may start the higher dose regimen no earlier than 2 days after they took their last dose. Dosing will then occur at least 3 days apart. Every 6 weeks thereafter, based on tolerability assessments, patients can be considered for further up titration as described below (Table 2). At each titration visit, the patient may start the higher dose regimen no earlier than 2 days after the prior dose.

Patients may titrate to a maximum dose of OCA 10 mg twice weekly at least 3 days apart.

Table 2: Planned OCA or Matching Placebo Dosing Regimen

	Child-Pugh B and Child-Pugh C (Moderate and Severe Hepatic Impairment)	
	Treatment Group	
	OCA	Placebo
Starting Dose (Day 1)	5 mg once weekly	matching placebo once weekly
Titration 1 ^a	5 mg twice weekly ^b	matching placebo twice weekly ^b
Titration 2 ^a	10 mg twice weekly ^b	matching placebo twice weekly ^b

^a Planned titration regimen is shown; however, the titration of dose and/or frequency is dependent on patient tolerability.

^b Dosing per the twice weekly schedule must be at least 3 days apart.

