7.5. Dose Titration Criteria

Dose titration may follow the scheduled dosing regimens described in Section 7.3 or occur due to tolerability concerns.

Dose titrations may involve increases or decreases in dosing frequency and are dependent on tolerability (as assessed by a review of AEs and safety laboratory results). In general, down-titration may be done in response to tolerability concerns and can occur at any time.

Up-titration will be done per protocol based on tolerability, as assessed by the Investigator based on response, or following resolution of a tolerability concern that previously led to down-titration. Up-titrations may only occur to the maximum dose and frequency indicated as defined in [Section 7.3](#).

Scheduled Dose Titration - After initiation of OCA or matching placebo, titration may be considered as early as the Week 12 Visit. Subsequent titrations in dose for patients may occur no earlier than 6 weeks following an up-titration.

Tolerability Dose Titration - Investigators may decrease the dosing frequency or dose as considered clinically appropriate (eg, tolerability).

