14.2.2. Markers of FXR activation

Blood samples will be collected in all patients to measure C4, FGF-19, and bile acids. The results of these analyses will be used to assess the PK/PD response of OCA. Blood samples will be assessed in patients according to the schedule presented in [Table 1](#).

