15.1. Analysis Populations

The following patient populations will be evaluated and used for presentation and analysis of the data:

- The Intent-to-Treat (ITT) Population will include all randomized patients who receive any amount of investigational product (OCA or placebo). The ITT Population will be the primary population used for summarizing efficacy assessments.
- The Safety Population will include all patients who received at least one dose of investigational product (placebo or OCA). The Safety Population will be the primary population used for safety analyses.
- The PK population will include all patients receiving OCA who have adequate concentration-time profiles to characterize OCA and its conjugates and must not have any major protocol deviations that potentially affect exposure levels.

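### The combined PK/PD set excludes placebo patients although their PD data exist at every PK visit, which makes time and exposure hard to separate

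*Protocol*

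**What the plan says.** Section 6.3 lists the PK/PD relationship among the additional objectives, as "PK parameters compared to PD parameters and safety and tolerability assessments". Section 12 fixes who enters: "Patients in the PK Population with at least one PD assessment after dosing will be included in the combined PK/PD analyses". Section 15.1 defines the parent set: "The PK population will include all patients receiving OCA who have adequate concentration-time profiles to characterize OCA and its conjugates". Read together, these leave no route for a placebo patient into the combined analysis.

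The placebo data exist. Section 14.2.2 states: "Blood samples will be collected in all patients to measure C4, FGF-19, and bile acids". It adds that the results serve to assess the PK/PD response. Table 1 and Section 12.1 place both PD and PK samples at Day 1 and Weeks 6, 12, 18, 24, 30, 36 and 48, in both arms.

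On dosing, Section 7.5 says: "After initiation of OCA or matching placebo, titration may be considered as early as the Week 12 Visit". Section 7.3 continues: "Every 6 weeks thereafter, based on tolerability assessments, patients can be considered for further up titration". The ceiling is given as "Patients may titrate to a maximum dose of OCA 10 mg twice weekly at least 3 days apart". Table 2 qualifies the scheme: "the titration of dose and/or frequency is dependent on patient tolerability".

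**The concern.** In the OCA arm, planned weekly dose can only go up on schedule, and it does so in the same weeks in which the disease runs its course. Section 5.5 describes PBC as chronic and progressive, so bile acids and liver-related safety measures may change over 48 weeks without any drug effect. A set with no concurrent zero-exposure patients has little with which to tell such change from a response to rising exposure. At stake is the exposure-response reading for Child-Pugh B and C patients, which Section 5.4.1 expects to inform how hepatically impaired patients are treated. The information that would separate the two is already being collected and is set aside for this analysis.

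**Working it through.** The protocol gives no figure for the PK/PD analysis, so there is none to reproduce. The size of the problem can be examined from the visit and dose schedules, with the remaining inputs assumed.

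**1. Confounding of dose with time.** Post-baseline PD visits (Table 1): weeks 6, 12, 18, 24, 30, 36, 48. Weekly dose at those samples on the earliest titration (Table 2, steps after the Week 12 and Week 18 visits): 5, 5, 10, 20, 20, 20, 20 mg.

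- Sum of weeks 174, sum of doses 100, sum of products 3030.
- Sxy = 3030 − 174×100/7 = 544.29
- Sxx = 5580 − 174²/7 = 1254.86
- Syy = 1750 − 100²/7 = 321.43
- r = 544.29 / √(1254.86 × 321.43) = 0.86

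Including Day 1 at dose zero, r = 0.90.

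**2. Slope without a time term.** Assume no drug effect and a linear drift of 1 unit over 48 weeks in both arms. If every patient follows the earliest schedule and exposure is proportional to dose, the expected slope per 20 mg/week is (544.29/321.43) × (20/48) = 0.71. The drift alone produces it.

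**3. Effect of optional titration and exposure spread.** Simulation, 25 per arm, 400 runs per row, same drift, no drug effect, change from baseline regressed on exposure. Mixed titration means 40% take two steps, 30% one and 30% none. Entries are mean slope per 20 mg/week-equivalent (SD over runs).

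| Titration; SD of log exposure | OCA only, no time term | OCA only + visit | OCA + placebo + visit | Ratio of last two SDs |
|---|---|---|---|---|
| all on schedule; 0.01 | 0.706 (0.146) | −0.548 (18.838) | 0.018 (0.231) | not identified |
| mixed; 0.01 | 0.442 (0.372) | −0.011 (0.509) | −0.001 (0.307) | 1.66 |
| all on schedule; 0.5 | 0.288 (0.197) | 0.023 (0.313) | 0.007 (0.174) | 1.80 |
| mixed; 0.5 | 0.250 (0.297) | 0.015 (0.346) | 0.013 (0.255) | 1.36 |
| all on schedule; 1.0 | 0.072 (0.110) | −0.003 (0.122) | −0.001 (0.097) | 1.26 |
| mixed; 1.0 | 0.088 (0.162) | 0.013 (0.167) | 0.008 (0.148) | 1.13 |

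Visit terms remove the bias once exposure varies between patients. What is left is a loss of precision.

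**4. Precision and coverage in a second setting.** Assumptions: 21 evaluable per arm (25 × 0.85 = 21.25, using the 15% discontinuation in Section 15.2), seven post-baseline visits, within-patient correlation 0.5, SD of log exposure 0.5, 20% Child-Pugh C at 13/8 of the Child-Pugh B exposure (the 13- and 8.0-fold plasma predictions in Section 5.4.2), no drug effect.

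- OCA only with visit terms: the SE of the slope is about 1.5 to 2.5 times that with placebo included, and about 1.2 to 1.9 times if the two-arm model also has an arm term. The ratio depends on the exposure scale: on log(1 + exposure) it reached 4.0 in the most extreme case.
- OCA only without a time term: a nominal 95% interval for the slope excludes zero in about 16–22% of trials at an assumed drift of 0.3 SD, and 37–48% at 0.5 SD.
- Both arms with visit terms: 4–7%.

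**The case against.** The strongest reply is that Section 12 fixes a set and not a model. Section 15.3 leaves PK methods to the SAP, and nothing in the protocol says that time will be ignored. A reader might infer that every change over time will be taken as an exposure effect; the documents do not support that. A reader might also infer that only placebo can separate time from exposure. That is too strong: titration is optional, depends on tolerability and can be reversed (Sections 7.5 and 8.4). Even on the fastest schedule, dose is flat from Week 24 to Week 48, and Child-Pugh B and C differ in predicted exposure. With visit terms the OCA-only slope is unbiased for shared drift.

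Some of the precision gained from placebo comes from the OCA-versus-placebo contrast carried through zero exposure, and shrinks when an arm term is added. Section 15 plans no formal hypothesis testing, so high false-positive rates cannot be claimed for this study; the percentages above describe interval coverage under chosen drifts. Section 15.5 compares C4, FGF-19 and bile acids between arms, where shared drift would show. PD is also not sampled at Week 3, Week 42 or in the extension.

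All of this stands, and it limits the point. It does not remove it: the set is written into Section 12, an SAP that added placebo patients would depart from it, and seeing drift in Section 15.5 does not correct an exposure slope estimated elsewhere.

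**Conclusion.** The point holds as a weakness in a stated analysis set, not as a demonstrated error in a stated analysis. With placebo excluded, time and exposure are strongly but not fully confounded (r = 0.86 on the earliest titration). The exposure slope is then either open to bias from shared drift, if time is not modelled, or unbiased for that drift but with an SE about 1.2 to 2.5 times larger than it need be. That range rests on assumed titration rates, exposure spread and exposure scale, and on whether an arm term is used; settings outside it can be constructed in both directions (1.13 and 4.0 above). The drift is assumed throughout, because the protocol gives none. Including placebo would not cure everything: when tolerability decides who is titrated, exposure is linked to how the patient is doing, and that confounding partly remains. This is a cheap and worthwhile improvement to an additional objective. It does not touch the PK summaries or the between-arm comparisons.

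**What to change.** In Section 12, define the combined PK/PD set as OCA patients in the PK Population, with their measured exposure, plus placebo patients with at least one post-dose PD assessment, with exposure set to zero. State that the model includes visit, baseline PD value and Child-Pugh class. Add one sensitivity fit, either the two-arm model with an arm term or the OCA-only model with visit terms, because a single exposure function running through zero is an assumption. Note that confounding by tolerability-driven titration remains when the results are interpreted. Keep the OCA-only PK Population for the PK parameter summaries.

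The cost is wording in Section 12 and matching text in the SAP. No sample, visit or patient is added. The small downside is the assumption about the exposure function, which the sensitivity fit is there to expose.

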12.1. Pharmacokinetic Blood Sampling

Serial and fasting PK assessments will be performed in all patients participating in the study.

[figure not shown]
At Day 1, and Weeks 6, 12, 18, 24, 30, 36, and 48, patients will provide fasted blood samples for measurement of OCA and its conjugates, glyco-OCA and tauro-OCA, and metabolite OCA glucuronide 30 minutes before administration of investigational product ([Table 8](#)). Patients will then receive a dose of investigational product with approximately 240 mL of water.

Week 6 Visit should occur 3, 4, or 5 days **after** the Week 6 dose (eg, if the Week 6 dose of investigational product is taken on a Sunday, the patient should come in for the Week 6 Visit between Wednesday and Friday [[Figure 3](#)]).

During the treatment period:

- Pharmacokinetic fasting samples will be obtained from all patients at Day 1, and Weeks 6, 12, 18, 24, 30, 36, and 48 prior to dose administration in accordance with [Figure 4](#).
- Serial PK assessments will be performed in all patients at Weeks 12, 18, 24, 30, and 48.

Figure 3: Week 6 Sampling Schedule

[figure not shown]

Week 6 Visit should be scheduled 3 to 5 days after the Week 6 OCA dose for collection of a single steady-state fasting PK sample

IP = investigational product; PK = pharmacokinetic

At Weeks 12, 18, 24, 30, and 48, serial PK blood samples will be obtained at 0.5, 0.75, 1, 1.5, 2, 2.5, 3, 4, 5, 6, 7, 8, 9, and 24 hours postdose (Figure 4) for all patients. The patient will be given the option to return to the clinic the following morning for the 24-hour postdose sample or samples can be obtained by a home health care designee. The home health care agency must be advised one week in advance of the appointment.

Figure 4: Pharmacokinetic Sampling Schedule

At meal timepoints, meals are consumed immediately after the collection of the PK sample

h = hour; IP = investigational product; PK = pharmacokinetic

Patients should not drink additional water for 1 hour after taking the dose of investigational product and will remain fasted until after the 1-hour sample is collected. A meal replacement drink will be provided following collection of the 1-, 4-, and 7-hour PK sample. The nutritional information of the meal replacement drink should be submitted to and approved by the Sponsor in advance. No other food or drink (water is permitted) will be allowed until after the 9-hour sample collection.

Table 8: Acceptable Windows for Pharmacokinetic Sample Collection

Nominal Sampling Time	Acceptable Sampling Window
Before administration of investigational product (predose or fasting)	Within 30 minutes before dosing
0.5 to 1.5 hours after investigational product	± 10 minutes
2 to 2.5 hours after investigational product	± 20 minutes
3 to 24 hours after investigational product	± 30 minutes

12.2. Processing and Handling of Pharmacokinetic Samples

Whole blood will be collected at each scheduled sample timepoint. Detailed procedures for the collection of blood samples including further processing into plasma will be provided in a separate laboratory manual. The storage and shipment procedures for subsequent bioanalysis, will be provided to the investigational site and home health care company in a separate document before the study is initiated.

12.3. Bioanalysis

Plasma concentrations of OCA and its conjugates, glyco-OCA and tauro-OCA, and metabolite OCA glucuronide will be determined using a validated liquid-chromatography mass spectrometry/mass spectrometry (LC/MS/MS) method. A detailed description of validation information and results from the bioanalytical assay will be provided in separate reports. These samples may be used for evaluation of metabolites of OCA or other concomitant medication, for further evaluation of the bioanalytical method, and for analyses that provide information on the metabolic pathways used or impacted by OCA.

13. ASSESSMENT OF SAFETY

13.1. Adverse Events and Serious Adverse Events

13.1.1. Definitions of Adverse Events

13.1.1.1. Adverse Event

AEs are defined as any untoward medical occurrence associated with the use of the investigational product in humans, whether or not considered related to investigational product. An AE, also referred to as an adverse experience, can be any unfavorable and unintended sign (eg, an abnormal laboratory finding), symptom, or disease temporally associated with any use of the investigational product, without any judgment about causality and irrespective of route of administration, formulation, or dose, including an overdose.

AEs include, but are not limited to: (1) a worsening or change in nature, severity, or frequency of condition(s) present at the start of the study; (2) patient deterioration due to primary illness; (3) intercurrent illness; and (4) drug interaction. For reporting purposes, pregnancy is not considered an AE.

Patients should be questioned about AEs in a general way, without leading the patient or asking about the occurrence of any specific symptom. The Investigator should attempt to establish a diagnosis of the event based on signs, symptoms, and/or other clinical information. The diagnosis and not the individual signs/symptoms should be documented as the AE. For example, if the underlying disease process is a stroke, it would not be appropriate to record the AE by describing the symptoms “sudden numbness, dizziness, and difficulty speaking.” The AE medical term of “stroke or cerebrovascular accident” should be recorded as it more accurately describes the AE.

Patients should be instructed to contact the site promptly upon awareness if they develop signs and symptoms of potential hepatic decompensation such as: pale-colored stools, urine color from pale to deep amber [dark], nausea, vomiting, abdominal pain, diarrhea, weight loss, fever and chills, fatigue, weakness, loss of appetite, confusion, swelling of the legs or abdomen, yellowing of the skin or the whites of eyes, and bruising easily.

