As of October 2018, greater than 4200 patients have received Ocaliva® in the post-marketing setting. In patients with moderate to severe hepatic impairment (Child-Pugh B and C), liver decompensation, liver failure, and death have been reported when Ocaliva was dosed up to 7 times the recommended once weekly starting dose for such patients. Based on the initial medical assessment of these cases, which included patients having undergone liver transplant, there was insufficient evidence suggesting a causal relationship between higher than recommended dosing and the reported adverse events. However, Intercept Pharmaceuticals, Inc. (the Sponsor) continues to assess the potential association between adverse events, including deaths, and the higher than recommended dosing of Ocaliva observed in PBC patients with moderate to severe hepatic impairment (Child-Pugh B and C) through ongoing post-marketing pharmacovigilance activities.

Signs and symptoms reported in patients experiencing liver-related adverse events who received Ocaliva include: increases in bilirubin and other liver enzymes, new or worsening pruritus, new

or worsening fatigue, vague neuropsychiatric symptoms (such as dysphoria), abdominal pain, nausea, vomiting, diarrhea, dehydration, jaundice, and liver decompensation.

Refer to the IB for additional information regarding the known potential risks with the investigational product.

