15.4.4. Adverse Events of Special Interest

Pruritus: Treatment-emergent pruritus, defined as any PT including “Prur,” will be summarized separately by the MedDRA SOC, treatment group, and PT as a subset of all TEAEs. This summary will be repeated for patients with “new or worsened” pruritus events, as defined as follows:

- Mild, moderate, or severe treatment-emergent pruritus events in patients with no pruritus at Baseline, or
- Worsening of the severity of the Baseline condition in patients with pruritus at Baseline.

Baseline pruritus is defined as the Investigator’s rating of severity as collected on the PBC Disease History eCRF. Patients whose Baseline severity is severe will be counted as worsening if an AE of pruritus with severe is recorded.

An analysis of treatment-emergent pruritus event days per patient years on study will be performed. The days at each severity grade, including the total days of event, the total patient years on study, and the event days per patient year on study at each severity grade, including the total, will be summarized. Each individual patient year on study will be derived as the last known date during the study minus the first dose date plus 1 divided by 365.25 days/year.

In order to explore the relationship between pruritus and the investigational product, the following time-to-event analyses will be performed:

- Time to first onset of treatment-emergent pruritus
 - The time to the start of the first episode will be calculated by date of onset of first episode – date of first dose of investigational product + 1.
 - Patients who never reported an AE of pruritus will be censored at the date of last contact.
- Time to onset of the first moderate or severe treatment-emergent pruritus
 - The time to the start of the first moderate or severe pruritus will be calculated by date of onset of the first moderate or severe pruritus – date of first dose of investigational product +1.

- Patients who never reported a moderate or severe AE of pruritus will be censored at the date of completion or discontinuation.
- Time to onset of the first severe treatment-emergent pruritus
 - The time to the start of the first severe pruritus will be calculated by date of onset of the first severe pruritus – date of first dose of investigational product +1.
 - Patients who never reported a severe AE of pruritus will be censored at the date of completion or discontinuation.

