The analysis of time to first onset of treatment-emergent pruritus AE, time to onset of the first moderate or severe treatment-emergent pruritus, and onset of the first severe treatment-emergent pruritus will include the number of patients with pruritus (first onset, first moderate or severe, first severe), the number of patients without pruritus (censored), and the minimum and maximum times in days. KM estimates will be calculated by treatment group. The tabulation will include the KM estimate methodology using 25th, 50th (median), and 75th percentiles of the medians and corresponding with associated 2-sided 95% confidence intervals (CIs), if the medians can be estimated as well as percentage of censored observations.

Fatigue: Treatment-emergent fatigue is defined as any PT which includes “Fatigue.” New or worsened treatment-emergent fatigue is defined as follows:

- Any mild, moderate, or severe treatment-emergent fatigue events in patients with no fatigue at Baseline, or
- Worsening of the severity of the Baseline condition in patients with fatigue at Baseline.

Baseline fatigue is defined as the Investigator’s rating of severity as collected on the PBC Disease History eCRF. Patients whose Baseline severity is severe will be counted as worsening if an AE of fatigue with severe is recorded.

An analysis of treatment-emergent fatigue event days per patient years on study will be performed. The days at each severity grade, including the total days of event, the total patient years on study, and the event days per patient year on study at each severity grade, including the total, will be summarized. Each individual patient year on study will be derived as the last known date during the study minus the first dose date plus 1 divided by 365.25 days/year.

In order to explore the relationship between fatigue and the investigational product, the following time-to-event analyses will be performed:

- Time to first onset of treatment-emergent fatigue
 - The time to the start of the first episode will be calculated by date of onset of first episode – date of first dose of investigational product + 1.
 - Patients who never reported an AE of fatigue will be censored at the date of last contact.
- Time to onset of the first moderate or severe treatment-emergent fatigue

- The time to the start of the first moderate or severe fatigue will be calculated by date of onset of the first moderate or severe fatigue – date of first dose of investigational product +1.

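### Recording the diagnosis in place of its symptoms, with no exception for pruritus and fatigue, can remove episodes from the term-based analyses in Section 15.4.4

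*Protocol*

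**What the plan says.** Section 13.1.1.1 sets the recording rule: "The diagnosis and not the individual signs/symptoms should be documented as the AE". It illustrates the rule with stroke and gives no exception for any symptom. The same section fixes how events are elicited: "Patients should be questioned about AEs in a general way, without leading the patient or asking about the occurrence of any specific symptom".

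Table 7 in Section 11 lists the assessments for the primary safety and tolerability objective as "SAEs and TEAEs, physical exam, ECG, vital signs, clinical laboratory assessments, discontinuations, pruritus, and fatigue".

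Section 15.4.4 sets the case definitions. For pruritus: "Treatment-emergent pruritus, defined as any PT including" the string Prur, and these cases "will be summarized separately by the MedDRA SOC, treatment group, and PT as a subset of all TEAEs". For fatigue: "Treatment-emergent fatigue is defined as any PT which includes" the word Fatigue. Baseline severity of each symptom is the Investigator's "rating of severity as collected on the PBC Disease History eCRF". For each symptom the section plans a new-or-worsened definition, event days per patient-year, and three time-to-onset analyses (any, moderate or severe, severe). Pruritus incidence is also tabulated.

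Section 5.6, describing post-marketing patients with liver-related adverse events, names among the reported signs and symptoms "increases in bilirubin and other liver enzymes, new or worsening pruritus", and new or worsening fatigue in the same sentence.

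**The concern.** The collection rule and the case definition pull in different directions. The rule favours one diagnostic term over its component symptoms. The analyses need the symptom to stand as its own term, with its own severity and start and stop dates. In Child-Pugh B and C patients, liver diagnoses are foreseeable, and the protocol itself reports both symptoms alongside liver-related events.

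At stake is the completeness of two tolerability assessments named under a primary objective. One of them, pruritus, is what Section 5.6 calls the primary adverse event related to OCA. This is a data-collection matter, so a statistical analysis plan cannot repair it: a term search does not find a row that the site was told not to enter.

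**Working it through.** The plan states no figure on this point, so there is nothing to reproduce. The check follows one episode through the relevant sections.

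1. **Can the symptom be attached to a liver diagnosis?**
   - Fatigue: yes, on the protocol's own lists. Section 7.4.1 includes it among the signs and symptoms of hepatic injury or decompensation, and Section 13.1.1.1 includes it among those of potential decompensation.
   - Pruritus: less clearly. It is on neither list. The link is the post-marketing description in Section 5.6, which shows that the two occur together and no more.
2. **What does the site enter?** If the Investigator attributes the symptom to the diagnosis and applies Section 13.1.1.1 literally, the diagnosis is entered and the symptom is not. General questioning without symptom prompts gives no second route to that term.
3. **What does Section 15.4.4 then see?**
   - Incidence: no matching term, so no case, unless the patient has another recorded episode of the same symptom.
   - New or worsened: baseline comes from a dedicated Investigator rating, but change after baseline is read only from adverse events, so there is no worsening.
   - Event days per patient-year: the episode adds nothing to the numerator. The denominator, (last known date − first dose date + 1)/365.25, is unchanged, so the rate falls.
   - Time to onset: a patient with no recorded event is censored at last contact (for moderate or severe and for severe pruritus, at completion or discontinuation), that is, analysed as event-free up to then.
4. **Is the symptom measured elsewhere?** Yes. Section 13.2.7 specifies a Pruritus VAS, the PBC-40 with Itch and Fatigue domains, and the CLDQ with a fatigue domain. Table 1 schedules them at Day 1, Weeks 6, 12, 18, 24, 30, 36 and 48, and every 3 months afterwards. They serve the additional objectives and are not inputs to Section 15.4.4. As visit-based scores they supply neither onset and stop dates nor an Investigator severity grade.

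**Scale.** Section 15.2 plans about 50 patients at 1:1, so about 50/2 = 25 per arm. Each patient whose every episode of a symptom is absorbed into a diagnosis lowers that arm's incidence by 1/25 = 4 percentage points; two patients, 2/25 = 8 points; three, 3/25 = 12 points.

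**Direction.** If equal numbers are lost in two arms of 25, both incidences are understated and their difference is unchanged. If more are lost in one arm, the difference shifts against that arm's true rate. The protocol gives no expected rate of pruritus, fatigue or liver events by arm, so neither the number nor the direction can be calculated.

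**The case against.** Several points count against the concern, and most of them narrow it.

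- Recording the diagnosis is a common convention, and the stroke example concerns symptoms that make up the diagnosis. It need not suppress every symptom present alongside one. Section 13.1.1.1 also defines an adverse event to include a symptom and the worsening of an existing condition. This stands as a reasonable reading, but the text does not tell sites which reading to use.
- For pruritus the route is weak. Section 5.6 reports no evidence that it is associated with disease stage or progression and treats it as an adverse event in its own right. Table 5 makes new onset severe pruritus a separate dose-adjustment criterion, so sites must identify it. This stands, and fatigue is the clearer case.
- Section 7.4.1 requires signs and symptoms of potential hepatic injury to be followed by documentation on the AE or SAE eCRF, which points away from loss of fatigue. It does not say that the symptom must be its own term, so Section 13.1.1.1 still governs how it is entered.
- The liver events themselves are not lost. Section 13.1.1.4 makes decompensation events adverse events of special interest, and Section 15.9 sends suspected liver-related events to blinded adjudication. Section 15.4 plans no formal testing of safety endpoints, so no decision rule changes. This stands and limits the consequence.
- The eCRF completion instructions are not at hand and may already contain the exception.

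A reader might infer that pruritus and fatigue are detected in this study only through adverse event terms. That is true of Section 15.4.4 but not of the study, because three questionnaires measure them independently of coding.

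**Conclusion.** The protocol has an unreconciled recording instruction. Applied literally, Section 13.1.1.1 can remove fatigue episodes, and less clearly pruritus episodes, from analyses that depend entirely on those terms being entered, and the affected patients would be analysed as free of the symptom. The effect on incidence is 4 percentage points per patient lost at about 25 per arm, and it requires that every episode of that symptom in that patient be absorbed.

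The conclusion rests on two conditions: the site attributes the symptom to the diagnosis, and it follows the rule as written. Two stronger conclusions are tempting. One is that such cases will drop out; the documents support only that they can, since Sections 5.6, 7.4.1 and Table 5 give sites reasons to record them separately. The other is that the loss makes OCA look better tolerated; that would need more absorbed cases on OCA than on placebo, and nothing in the protocol gives those rates. The point merits correction because both symptoms are named under a primary objective and the loss cannot be recovered after collection.

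**What to change.** Add one exception to Section 13.1.1.1: new or worsened pruritus and fatigue are always recorded as their own adverse event terms, with their own severity and start and stop dates, in addition to any underlying diagnosis. Align the AE documentation wording in Section 7.4.1 so that it says the same, and carry the sentence into the eCRF completion guidance. As a check on completeness, compare the Section 15.4.4 counts with the Pruritus VAS and the PBC-40 Itch and Fatigue domains.

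The cost is one sentence, a matching edit and site guidance. The downside is slightly more adverse event rows in both arms, some of them describing a symptom of a diagnosis that is also listed.
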